# 3.2.3 Quality of Life

PROMIS forms will be administered to assess various aspects of quality of life (Appendix E) Versions of the PROMIS measures include adult self-reports for 18+ years, pediatric self-reports (ages 8 to 17 years), and parent reports for youth less than 18 years of age. Items ask the respondent to indicate the extent to which they have had particular problems over the past week, using a 1 - 5 Likert scale. The subscales that will be administered on this study include Depression (8 items on self-reports, 6 items on parent report), Pain Interference (6 items on adult self-report, 8 items on pediatric self-report and parent report), and Cognitive Function (8 items on adult self-report, 7 items on pediatric self-report and parent report). Mean scores for each subscale are converted to T-scores, and then can be compared to a mean of 50 and standard deviation of 10. These subscales should take about 10 minutes to complete. A score of 70 or higher on the PROMIS Depression scale will result in the Adherence Study PI or an AI, or the study team member for the primary medical protocol to talk (by phone or in person) to the patient/caregiver about this and may necessitate a referral to an outside mental health professional.

# 3.2.4 Generic Medication Diary Form

To be completed by adult patients or caregivers of pediatric patients as the medication is taken and returned to primary study team at each clinical protocol re-staging visit (same visits at which the MEMSTM cap data will be retrieved). If the clinical trial on which the patient is enrolled has its own patient diary form, this can be used in place of the generic form provided in **Appendix G**.

# 3.2.5 Pill Count Form

This form is to be completed by the study team at the time of each clinical protocol re-staging visit (same visits at which the MEMSTM cap data will be retrieved).

# 3.2.6 Barriers to Adherence Questionnaire

The Barriers to Adherence Questionnaire includes a list of common reasons why people might miss a dose of medication. The respondent is asked to check any items that caused the patient to miss a dose of the NF study medication in the past month. The form will be sent electronically via a link to a secure site (Scribe) to patients when MEMSTM data show adherence to be less than 90%. The form will be sent as close in time as possible (ideally within one week and if feasible within one month) of the data being reported to the study team. At the end of the study, any patients who had not previously completed the Barriers to Adherence Questionnaire will be asked to do so. Reminders will be sent if patients do not respond within one week (phone and/or email). If participants do not complete the questionnaire after three prompts, we will document the noncompletion and these data will be used in consideration of feasibility. There is an adult

self-report version, a child self-report version (ages 8 and up) and a parent version (parents of children 3 - 17 years). These forms are in Appendix F.

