## **3.3 Study Calendar**

 Will be given to patients/caregivers at baseline to complete only when pill bottle openings do not correspond to medication taking (**Appendix I**).

 Will be sent electronically to any subject who has < 90% medication adherence documented by MEMSTM systems (**Appendix F**). This questionnaire may be sent to a single subject more than once (each time adherence < 90% is identified). All patients will be sent the questionnaire after 18 cycles of treatment or at the time patient comes off treatment trial (whichever comes first).

 To be performed with primary caregiver of patients 3-18 and patients ages 18+ any time between cycles 8 and 12.

<sup>1To be completed by the patient and/or caregiver. Can use the Generic Medication Diary Form (Appendix G) or treatment protocol specific diary form

<sup>2 To be completed by the study team at the time of routine protocol re-staging visit (**Appendix K**)

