# 6.2 SECONDARY ENDPOINTS

- 6.2.1 Average percent adherence based on the MEMSTM data only for cycles 1-4, 5-8, 9-12 and 13-18
- 6.2.2 Relationships between adherence (correlations, t-tests, etc.) and demographics, life events and barriers to adherence will be used to identify patient characteristics that may predispose to poor medication adherence

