## 6.5 ANALYSIS OF THE SECONDARY ENDPOINTS

The first secondary objective is to evaluate medication adherence over time in patients with NF1 receiving oral medications for treatment of plexiform neurofibroma(s) on a clinical trial. The reported results using the MEMSTM data will also be compared to that obtained via pill counts and patient diaries. Patients assigned drug holds by the study team that cover more than 50% of originally prescribed doses within any consecutive 3 months may be excluded from analyses that examine patterns of adherence over time. We may do separate exploratory analyses looking at longitudinal adherence among those with extensive drug holds depending on how many patients constitute this group by the end of the study.

As an additional secondary objective, we will determine the factors (demographics, QOL, etc) related to adherence. To do this, we will conduct bivariate correlations or analysis of variance between MEMS

adherence rates and demographics, PROMIS t-scores, and barriers most frequently endorsed on the barriers questionnaire.

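### Barriers can be ticked only if they caused a missed dose, so correlating them with MEMS adherence (6.5) is circular and cannot show predisposition (6.2.2)

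*Combined protocol and SAP*

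**What the plan says.** Section 3.2.6 describes the barriers form: the respondent is "asked to check any items that caused the patient to miss a dose of the NF study medication in the past month". Section 1.2.3 defines MEMS adherence as doses taken divided by doses prescribed, as a percentage.

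For the secondary objective on predisposing factors (1.1.2.2), section 6.5 plans simple correlations or an ANOVA linking the cap-measured "adherence rates and demographics, PROMIS t-scores, and barriers most frequently endorsed on the barriers questionnaire". Section 6.2.2 gives the intended reading: "life events and barriers to adherence will be used to identify patient characteristics that may predispose to poor medication adherence".

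The plan describes delivery of the form in several ways.

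- **End of treatment.** Sections 1.2.3, 3.1 and 3.2.6 limit the final form to those without an earlier one: "any patients who had not previously completed the Barriers to Adherence Questionnaire will be asked to do so". Footnote 4 of the study calendar (3.3) says "All patients will be sent the questionnaire after 18 cycles of treatment", or on leaving the treatment trial if that comes first.
- **Trigger.** The précis uses MEMS adherence below 90% at a study visit. Section 1.2.3 uses below 90% in one or more cycles, or below 80% by another method. Sections 3.2.6 and 3.3 mention MEMS only.
- **Repeats.** Section 3.3 adds: "This questionnaire may be sent to a single subject more than once (each time adherence < 90% is identified".
- **Respondent.** Besides the adult form there is "a child self-report version (ages 8 and up) and a parent version (parents of children 3 - 17 years". Section 6.5 does not say which version enters the analysis.

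**The concern.** Missed doses determine the outcome, and they also decide whether the predictor can be anything other than zero. A truthful tick is a reason for a dose already missed. It says nothing about whether patients with that barrier are more likely to miss doses than patients without it, because someone who faces the same barrier and still takes every dose cannot tick it. The baseline measures (demographics, life events, PROMIS) are not defined by missed doses and do not have this problem.

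Followed as written, section 6.5 would tend to present the commonest reasons as correlates of low adherence even if none of them separates patients. Section 1.2.2 wants such results to guide later interventions, so the artefact could misdirect them. The delivery gaps are separate, but they would blur even a descriptive table. If the final form goes only to patients without an earlier one, triggered patients report on a low-adherence period and everyone else on their last month. A patient aged 8-17 can also contribute two forms.

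**Working it through.** The plan gives no effect size, significance level or power for this analysis, so there is no figure of its own to reproduce.

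**1. Closed form, adherence measured in the recalled month.** Let z patients have no missed dose, m have at least one, and t of the m tick a given item at random. A ticker is less adherent than all z patients, and less adherent than half of the other m - t on average:

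P(ticker less adherent than non-ticker) = [z + (m - t)/2] / (z + m - t)

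With 15 patients (the accrual ceiling in 6.7) and t = 3 (assumed):

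- m = 6: (9 + 1.5)/12 = 0.88
- m = 8: (7 + 2.5)/12 = 0.79
- m = 10: (5 + 3.5)/12 = 0.71

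With no link the value is 0.50.

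**2. Miss rates in the preliminary data (1.2.2.2).** Twice-daily dosing over 28 days is 56 doses per cycle. The section reports 0.5% of doses missed in cycle 1 and 1.3% in cycle 18. It also reports 1.3 missed doses per cycle early on (1.3/56 = 2.3%) and 2.7 later (2.7/56 = 4.8%). In all, 16 of 23 patients (70%) missed any dose.

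**3. Simulation with no barrier special.** From the documents: n = 12 or 15, 18 cycles of 56 doses, visits as in 1.2.3. Assumed:

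- Ten items, and one end form for everyone.
- Beta-distributed miss rates per patient, with means of 1.3%, 2.5% and 3.5%. Concentrations of 24.2, 10.2 and 6.6 are set so that 7 of 23 patients miss nothing in 18 × 56 = 1,008 doses.
- A higher set with means of 5% and 10% (concentration 5 or 15), because 1.2.2.1 says diaries and pill counts overestimate adherence.
- A tick chance q of 20% or 30% if any dose was missed in the last cycle, or q/3 per missed dose.

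There were 500 runs per setting. The table gives the mean Spearman correlation for the most-ticked item. The control item can be ticked without a missed dose.

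| Doses missed | Whole-trial adherence | Last-cycle adherence | Control item |
|---|---|---|---|
| 1.3-3.5% | -0.43 to -0.62 | -0.55 to -0.76 | -0.02 to 0.02 |
| 5-10% | -0.09 to -0.66 | -0.11 to -0.76 | -0.04 to 0.03 |

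At the lower rates, 4.7-6.3 of 15 patients have a miss in the last cycle. Counting an item as ticked if it was ever ticked on a triggered or end form gives -0.45 to -0.67 at the lower rates and -0.42 to -0.74 at the higher ones.

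**4. A different mechanism.** Here each missed dose draws its reason from one distribution common to all patients, with 8 items, mean adherence 80-98% and Pearson correlation. The mean correlation with the most-ticked item is about -0.41 to -0.67. Restricting to patients with a miss in the last month leaves about -0.20 to -0.46, because more missed doses give more chances to tick.

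**5. Trigger wording (MEMS part only).** Expected number of 15 patients ever triggered:

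| Doses missed | Below 90% at a visit (précis) | Below 90% in any cycle (1.2.3) |
|---|---|---|
| 1.3-3.5% | 0.4-2.1 | 1.3-3.5 |
| 5-10% | 2.8-7.4 | 4.3-11.0 |

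**The case against.** The strongest reply is that the plan claims little. Section 6.6 calls all other secondary and exploratory analyses descriptive, 6.2.2 speaks only of what may predispose, and no decision hangs on the result in 12-15 patients. That limits the consequence. It does not remove the problem: 6.5 names correlation or analysis of variance, and a correlation reported descriptively is just as circular.

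Second, the form recalls one month, while adherence is summarised over blocks of cycles or the whole trial. The closed form applies strictly to the recalled month, and its middle case (8 of 15) lies above the 4.7-6.3 expected at the preliminary rates. Both points stand. The simulated whole-trial probability at those rates with 15 patients is nevertheless 0.83-0.92, so the closed form does not overstate there.

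Third, the size depends on assumptions. At 10% missed with concentration 15, the any-miss tick rule gives only about -0.10, because nearly everyone has a miss to explain, while the per-dose rule gives about -0.44. The documents favour neither rule. This stands, so the size is best read as a range.

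Fourth, Appendix F is not in the available text, so the item wording rests on the description in 3.2.6. That description is explicit, but the form itself should be checked.

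Finally, a recurring reason may also be a predisposing factor. It may, but this form cannot show it.

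**Conclusion.** The concern holds. By the form's description, only a missed dose permits a tick, so the barrier analysis in 6.5 has a negative expected association built in and cannot support the reading in 6.2.2. This is a bias in the expected value, not a guaranteed sign in every sample, and more patients would not remove it.

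At miss rates in line with the preliminary data, the artefact alone is about -0.4 to -0.6 for whole-trial adherence. At 5-10% missed it runs from near zero to about -0.66, weakest when almost everyone misses a dose. These sizes assume the stated tick rules and that respondents' reports of missed doses agree with the caps.

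The effect is confined to one secondary analysis. The gaps in end-form recipients, trigger and respondent version are real but separate, and closing them would not cure the circularity. The change should be made, but it does not threaten the study.

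**What to change.** 1. In 6.5 and 6.2.2, remove barriers from the correlation or analysis of variance with MEMS adherence. Report them descriptively as reasons given for missed doses, separately for triggered and end-of-treatment forms and for adult, child and parent versions, with the number completing each form as denominator.
2. Keep the correlations for demographics, life events and PROMIS scores. Align the two lists in the same edit: 6.2.2 names life events but not PROMIS, and the analysis sentence in 6.5 does the reverse.
3. Reconcile 1.2.3, 3.1 and 3.2.6 with footnote 4 of 3.3 on who receives the end form, so that all patients share a time point.
4. Reconcile the trigger between the précis and 1.2.3, and carry the result into 3.1, 3.2.6 and 3.3.

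The cost is wording and no new data. Section 3.3 already sends the end form to everyone, and 6.6 already favours description. What is lost is a formal test of barriers against adherence; the interviews (3.2.8) still cover barriers qualitatively. If such a test is wanted, barriers would have to be asked about regardless of missed doses, at baseline, and related to later adherence. That would mean new data collection.

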# 3.2.7 MEMSTM Recording Form

This form allows adult patients or caregivers of pediatric patients to record any times at which MEMSTM bottle openings do not correspond to doses taken. For example, patients may indicate that they removed their AM and PM doses in the morning because they were not going to be home at the time of the PM dose. Adjustments to the MEMS data may be made in accordance with the data on this form. See **Appendix I**.

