## 1.2.2.1 Medication Adherence Monitoring

Most clinical trials that currently attempt to monitor adherence utilize self-reported patient diaries and researcher-performed pill counts to do so; however, extensive prior research  and our experience with these methods has shown them to be inconsistent and to overestimate adherence. One method for more objective monitoring of adherence is the use of a medication event monitoring system (MEMSTM). Through a microchip implanted in the pill bottle cap, this system uses a computerized method of tracking the dates and times of the pill bottle being opened. A recent Children's Oncology Group Study that compared reporting of maintenance 6-MP medication adherence by self-reported diaries with MEMSTM data showed that 23.6% of 416 patients over-reported their adherence (self-report was higher than MEMS by  $\geq$  5 days/month for  $\geq$  50% of study months).

Use of MEMSTM among patients on NF1 clinical trials would allow us to more accurately track adherence to document patterns of change over time, and would allow us to more fully assess if there is any correlation between tumor response and medication adherence.

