Patients/caregivers will be given a form to complete any time they take a dose of medication that does not correspond to a pill bottle opening (Appendix I) Patients will also be asked to complete a self-report daily diary of medication adherence throughout treatment or through 18 cycles of therapy (whichever is shorter) and pill counts will be performed at all standard treatment protocol visits during this time. If diaries are included on the primary treatment protocol, these will be utilized. If not, a generic diary (Appendix G) form will be provided. The pill count form (Appendix H) should be completed by the study team for each cycle for all participants, as this also contains information regarding any dose adjustments or changes. These forms should be collected/completed by the study team during each routine treatment protocol mandated follow up appointment. In addition, at these visits patients will return their MEMSTM caps and data from the caps will be uploaded onto a computer software system before being returned to the patient during that same visit. Although not anticipated, if there are scheduling difficulties prohibiting the return of the cap before the patient leaves the center, we will send the cap to the patient/family via Federal Express. It is recommended, but not required, that a patient bring their MEMS cap to any of these visits, if a patient forgets we will collect the data at the next visit during which they bring the cap to clinic.

Results of evaluations for disease response as per the primary treatment protocol will be recorded (e.g. tumor volume) at all restaging evaluations through 18 cycles of therapy. The response criteria defined by each specific treatment protocol will be used to determine if the patient had stable disease, partial response, complete response or disease progression while on study therapy.

[figure not shown]
Following each study visit, rates of adherence from the diaries, pill counts, and MEMS caps will be compared. If one or more methods suggest an adherence rate of less than 80%, the PI of the medical trial will be notified via secure email or phone.

Patients with MEMS cap data indicating <90% adherence will be sent a Barriers to Adherence Questionnaire (Appendix F) electronically as close in time as possible (ideally within one week

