# 6.6 ANALYSIS OF EXPLORATORY ENDPOINTS

Patients who are enrolled onto this trial will have the fraction of the total times that their medication is intended to be taken determined and reported with descriptive statistics based on results obtained using the MEMSTM system. This will be determined per patient as a percentage of the total planned medication administrations during all doses for which the patient is enrolled on the trial and eligible to be receiving medication. All study team directed medication holds and/or dose changes will be documented on the Pill Count Form (**Appendix H**) and will be used to determine the total planned medication administrations.

For each patient, there will be a percentage of total planned medication administrations calculated separately for cycles 1-4, cycles, 5-8, cycles 9-12 and cycles 13-18. Despite the limited number of patients to be enrolled, paired difference in the percentages between cycles 1-4 vs. 5-8, cycles 9-12 vs. 13-18, and cycles 1-4 vs. 9-12 will be formed for all patients during all evaluable cycles and reported using descriptive statistics. The calculated differences in adherence rates between time points will also be tested for being equal to zero using a Wilcoxon signed rank test, and interpreted as exploratory because of the limited amount of data.

The adherence rates as determined by the pill counts and the patient diaries will be recorded, and the agreement between these two measures and the MEMSTM percentages will be evaluated using exploratory and descriptive statistical methods. For example, the difference between two measures reporting the fraction of intended doses for a given set of three cycles will be reported and may be displayed graphically or formally tested using a paired analysis.

The analyses for all other secondary and exploratory objectives will be descriptive. Graphical presentations, such as histograms, stem and leaf plots, and scatterplots may be generated as appropriate to the type of endpoint.

- Transcriptions of individual interview will be created and analyzed descriptively using NVivo software.
- We will calculate and describe the percent medication adherence as documented by pill count, patient diary and using the MEMSTM system

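### MEMS rates may be adjusted at discretion from a self-report form, and Section 6 does not say whether raw or adjusted rates are analysed

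*Combined protocol and SAP*

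**What the plan says.** Section 1.2.2.1 explains why MEMS is used. Of diaries and pill counts, it says that prior research and the team's experience "has shown them to be inconsistent and to overestimate adherence". MEMS is offered as the more objective record.

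Section 3.2.7 adds a recording form: "This form allows adult patients or caregivers of pediatric patients to record any times at which" openings and doses do not match. It then says: "Adjustments to the MEMS data may be made in accordance with the data on this form". Its one example is a patient who takes out the morning and evening doses together. Section 3.1 describes the same form more narrowly, for use "any time they take a dose of medication that does not correspond to a pill bottle opening".

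The generic diary (3.2.4) has the same respondents: "To be completed by adult patients or caregivers of pediatric patients as the medication is taken". On collection, Section 3.1 says: "These forms should be collected/completed by the study team during each routine treatment protocol mandated follow up appointment". It has the three adherence rates compared after each study visit.

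Section 6.6 plans the method comparison: "the agreement between these two measures and the MEMSTM percentages will be evaluated". Objective 1.1.3.1 and Sections 6.3.1 and 6.5 call for the same comparison. Section 6.2.1 bases the cycle-window averages on MEMS data alone, and 6.3.2 splits patients at 90% by MEMS. Section 6 nowhere mentions the form or the adjustment.

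**The concern.** MEMS is in the study as a check on self-report. A dose credited to MEMS because the patient or caregiver wrote it on a form is itself self-report, from the person who also fills in the diary. If such credits enter the MEMS rate and that rate is then compared with the diary, the errors of the two methods are no longer separate, and agreement can look better than it is.

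The adjustment is optional. The available text gives no acceptance criteria, names no decision maker and does not ask for an unadjusted analysis. Two analysts could derive different rates from the same caps and forms. Section 6.6 is explicit about the denominator (team-directed holds and dose changes, taken from the Pill Count Form) but gives no rule for form-based changes to the numerator.

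At stake are the exploratory method comparison, the secondary window averages, the 90% response groups, the 90% trigger for the barriers questionnaire, and the MEMS part of the 80% notification.

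**Working it through.** **The plan's own figure.** The only design probability that the plan computes is in Section 6.7: at least 9 successes in 12 when the true rate is 50%. The exact tail is (220 + 66 + 12 + 1)/4096 = 299/4096 = 0.0730, which matches the stated 7.3%. Nothing below depends on it.

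**Which version of MEMS is analysed?**

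| Use of MEMS | Section | Raw or adjusted? |
|---|---|---|
| Comparison after each visit | 1.2.3, 3.1 | not stated |
| Method agreement | 6.3.1, 6.5, 6.6 | not stated |
| Cycle-window averages | 6.2.1, 6.6 | not stated (6.2.1: MEMS data only) |
| 90% response groups | 6.3.2 | not stated |
| Barriers questionnaire below 90% | 1.2.3, 3.1, 3.2.6 | not stated |
| Notification below 80% | 1.2.3, 3.1 | not stated |

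**Sensitivity of the 90% cut.** Section 1.2.3 defines adherence as doses taken divided by doses prescribed, times 100. Doses per cycle are an assumption, because the study is open to different treatment trials. The phase I schedule in 1.2.2.2 (twice daily, 28-day cycles) gives 2 × 28 = 56. Once daily gives 28.

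- Twice daily, one cycle: 50/56 = 89.3%, below the cut; 51/56 = 91.1%, above it. One accepted entry changes the class.
- Once daily, one cycle: 25/28 = 89.3%; 26/28 = 92.9%. Again one entry is enough.
- Twice daily, cycles 1-4: 4 × 56 = 224 doses. A raw rate of about 85% is 190 doses, with 224 − 190 = 34 missed openings. Reaching 90% needs 202 doses (202/224 = 90.2%; 201/224 = 89.7%), so 202 − 190 = 12 credits, or 12/34 = 35% of the missed openings.

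The one-cycle result bears directly on Section 1.2.3, where a single cycle below 90% triggers the questionnaire. Section 6.3.2 does not say over what period its 90% is measured; over longer periods more credits are needed.

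**Effect on the MEMS-diary gap (illustration).** Let *d* be the diary rate, *m* the raw MEMS rate, and *f* the share of diary-claimed doses without an opening that the form credits. Then adjusted MEMS = *m* + *f*(*d* − *m*), and the remaining gap is (1 − *f*)(*d* − *m*). With *d* assumed to be 98%:

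| Raw MEMS | *f* = 0 | *f* = 0.25 | *f* = 0.5 | *f* = 1 |
|---|---|---|---|---|
| 80% | 18.0 | 13.5 | 9.0 | 0 |
| 85% | 13.0 | 9.75 | 6.5 | 0 |
| 90% | 8.0 | 6.0 | 4.0 | 0 |

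Entries are percentage points. The table shows shrinkage of the gap, not bias. Only credited doses that were not in fact taken make the agreement false. At raw 85% and *f* = 0.5 the gap shrinks by 13.0 − 6.5 = 6.5 points, and the false part lies between 0 (all credits genuine) and 6.5 (none genuine). The documents give neither *f* nor the genuine share.

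**The case against.** The strongest reply is that adjustment is sometimes right. In the plan's own example, two doses leave the bottle at one opening, so raw MEMS is too low and the correction moves it towards the truth as well as towards the diary. Relying on the raw rate alone would count each such dose as diary over-reporting. This stands, and it is why both rates are needed.

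Four stronger readings are tempting, but the documents do not support them:

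- *MEMS is adjusted before it is compared with the diary.* The timing allows this, since forms are collected at visits and rates compared afterwards, but no section says which version is compared.
- *The raw record is lost.* Section 3.1 has cap data uploaded to software, and nothing says that openings are overwritten. The gap is that no unadjusted analysis is planned.
- *Adjustment only raises MEMS.* Section 3.1's wording points upward. Section 3.2.7 and footnote 3 of the study calendar cover any mismatch, which includes openings without a dose.
- *The cited leukemia study sizes the effect.* Section 1.2.2.1 reports that it "showed that 23.6% of 416 patients over-reported their adherence", by at least 5 days a month in at least half of months. That is diary excess over MEMS in another disease, not a rate of form entries. Turning it into a shift in MEMS here would assume that every over-report is also entered on the form and accepted.

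The reach is also limited. The method comparison is exploratory, in 12 to 15 patients. Pill counts are done by the study team and do not come from the form. Every patient is asked for the barriers questionnaire by study end, and the 80% notification fires on any one method. Appendix I was not in the text reviewed, so acceptance rules printed there cannot be ruled out.

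**Conclusion.** The point holds as a gap in the analysis plan. Section 3.2.7 permits discretionary, self-report-based changes to MEMS, and Section 6 does not say which version is analysed or require the unadjusted one. If the adjusted rate is set against the diary, agreement may be overstated, by an amount that the documents cannot fix. The firm numerical result is the fragility of the 90% cut within a cycle: one accepted entry can reclassify it, under either once-daily or twice-daily dosing over 28 days.

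The primary endpoint, the proportion of patients with at least two full cycles of recorded data, is not affected. The point is a cheap improvement that protects objective 1.1.3.1 and makes the MEMS summaries reproducible.

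**What to change.** In Sections 3.2.7 and 6.6:

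1. Derive both an unadjusted and a form-adjusted MEMS rate for every patient and cycle window.
2. Report MEMS-diary and MEMS-pill-count agreement with both rates.
3. Predefine which form entries are accepted, and have the decisions made without sight of the diary.
4. State which rate feeds the window averages, the 90% split, the barriers trigger and the MEMS part of the 80% notification.
5. Report the number and direction of adjusted doses per patient.
6. Bring the descriptions of the form in 3.1 and 3.2.7 into line, and check that Appendix I agrees.

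The cost is some added wording and one extra set of results; no new data are collected from patients. The raw rate understates adherence when doses are removed early, which is the reason for showing both.
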